**Urine**

PK parameters will be computed from the individual urine concentrations using a noncompartmental approach. Appropriate validated PK software (eg, WinNonlin Professional) will be used.

U e	The amount excreted in urine during the collection interval (C urine ), calculated as C urine x urine volume.
CL r	Renal clearance, calculated as CL r = U e /AUC 0-t . CL r will be calculated for the collection interval.
% Dose	The percentage of drug recovered in urine, calculated as (Cum Ue )/Dose x 100.

**8.2.6 Biomarker Analysis**

Biomarker assessments are secondary study objectives and will be performed on the ITT population to the extent data is available. The mean microvascular blood flow measurement and biomarker measurements of adhesion, and inflammation will be summarized by treatment group and time point. If there are enough data, these outcomes will be analyzed using a linear mixed model similar to hsCRP analysis.

**8.2.7 Study Drug Interim Analysis**

An interim safety review will be performed by the DSMB and Sponsor Medical Monitor after treatment of the first 10 subjects under 18 years of age, and additionally after 25 and 50 subjects of all ages have been treated with the study drug. This review will include AEs and any other pertinent information. The DSMB and the Sponsor's Medical Monitor will review select data listings to ascertain the existence of any safety concerns for which the study should be terminated, as described in Section 6.3.6.4. The Sponsor's Medical Monitor will remain blinded.

In addition to the safety review, the DSMB and a sponsor representative (not otherwise involved in the study execution) will also review the efficacy (clinical activity) results in the first 50 subjects. Stopping criteria for the efficacy interim analysis are discussed in Section 8.3.2.

**8.3 Statistical Considerations****8.3.1 Missing, Unused, or Spurious Data**

Subjects who drop out of the study will not be replaced. All efficacy, safety, PK, and clinical activity data collected will be used to the extent possible. Analysis of improvement in pain is based on the assumption of a normal distribution and no censoring. If there are many subjects who withdraw from study prior to discharge, the survival analysis that takes censoring into account will be performed instead.

The additional clinical activity analyses using a longitudinal mixed model allow for missing data and do not require eliminating the subject for missing data.

### **8.3.2 Sample Size**

Evaluable subjects are those who have received at least 1 dose of study medication. Subjects in the evaluable population will be used to determine when an adequate sample size has been achieved.

The study will enroll until a total of approximately 76 evaluable subjects (defined as those who have received at least 1 dose of study medication) have been enrolled. An interim analysis will be done after the first 50 subjects have completed the follow-up day 7 post last dose, to assess safety and efficacy. The efficacy test statistic for this interim analysis will be compared to a critical value corresponding to a 2-sided alpha of 0.005. To control study wise Type I error, an alpha spending approach will be utilized. The final analysis will then compare the test statistic to a critical value corresponding to 2-sided alpha of 0.045. Futility criteria will also be considered; these will be specified in detail in the statistical analysis plan.

A previous pilot study of treatments for pain in SCD showed the mean pain duration in placebo group is 103 hours with a standard deviation of 60 hours. The original protocol sample sizing was done as follows. Assuming that the variances are the same in both groups and anticipating that the study drug will decrease pain duration by 40%, a total of at least 76 subjects (38 subjects each group) will be needed to detect a 40% decrease in VOC resolution and to achieve 83% power with a 2-sided alpha of 0.045.

With the addition of a second dose level, the power calculation for the study has been updated to compare the treatment difference between the placebo group and the pooled active group (ie, both dose levels combined). The sample sizing assumes that the placebo group has a mean pain duration of 103 hours with a standard deviation of 60 hours, and that both groups – placebo and pooled active groups – share a common standard deviation. Anticipating that the placebo and pooled active groups will each have about 38 subjects (ie, the pooled group will have 19 subjects from each of the dose levels) the study will have an 89% power to detect a 43.8% decrease in VOC duration with a 2-sided alpha of 0.045.

The sample size is also expected to provide initial safety and PK conclusions sufficient to contribute to the design of subsequent trials.

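### Section 8.3.2 names alpha spending but fixes the final test at a nominal 0.045, a Bonferroni-type split that is valid but slightly conservative

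*Protocol*

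**What the plan says.** All the relevant text is in Protocol section 8.3.2 (Sample Size).

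- Final size: "The study will enroll until a total of approximately 76 evaluable subjects".
- Interim timing: "An interim analysis will be done after the first 50 subjects have completed the follow-up day 7 post last dose, to assess safety and efficacy".
- Interim boundary: "The efficacy test statistic for this interim analysis will be compared to a critical value corresponding to a 2-sided alpha of 0.005".
- Method: "To control study wise Type I error, an alpha spending approach will be utilized".
- Final boundary: "The final analysis will then compare the test statistic to a critical value corresponding to 2-sided alpha of 0.045".

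Both power statements use 0.045 as the test level. The first says that 76 subjects are "needed to detect a 40% decrease in VOC resolution and to achieve 83% power with a 2-sided alpha of 0.045". The second, updated for the pooled active group, says "the study will have an 89% power to detect a 43.8% decrease in VOC duration with a 2-sided alpha of 0.045".

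The section gives no overall alpha, names no spending function and does not say how 0.045 was obtained. It leaves the futility criteria to the SAP but states both efficacy boundaries itself.

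**The concern.** In an alpha spending design, the alpha left after the interim is not the nominal level of the final test. The final critical value comes from the joint distribution of the two test statistics, so that the probability of crossing at either look equals the overall level. Because the looks share data, the final nominal level can be higher than the alpha that remains. Here the final level equals 0.05 minus 0.005, which is what a Bonferroni split gives. The method named and the boundary fixed therefore do not match.

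Two things are at stake. First, an analyst who follows the named method with a 0.05 target would derive a final level near 0.049, while one who follows the printed figure would use 0.045. A final p-value between the two would be read differently, so the choice should be settled before any efficacy data are seen. Second, a little power is lost in a study of about 76 subjects.

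**Working it through.** **Inputs, all from Protocol section 8.3.2 unless noted.** Two-sided levels 0.005 (interim) and 0.045 (final); 50 subjects at the interim and about 76 at the end; 38 per group; placebo mean 103 h, SD 60 h; reductions of 40% and 43.8%. Section 5.1.4 gives 1:1 allocation. Section 8.2.3.1 expects no censoring, so information is taken as proportional to the number of subjects. **Assumed:** an overall two-sided alpha of 0.05.

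**Step 1. Reproduce the stated power.** Differences: 0.40 × 103 = 41.2 h and 0.438 × 103 = 45.1 h. Standard error: 60 × √(2/38) = 13.76 h. Noncentrality: 41.2/13.76 = 2.99 and 45.1/13.76 = 3.28. With the noncentral t on 74 degrees of freedom at two-sided 0.045, power is 82.8% and 89.0%. These round to the stated 83% and 89%, so the figures are right for a nominal 0.045.

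**Step 2. Correlation between looks.** Information fraction 50/76 = 0.658; correlation √0.658 = 0.81.

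**Step 3. Overall level of the stated pair.** Critical values: z = 2.807 for 0.005 and z = 2.005 for 0.045. For (Z1, Z2) bivariate normal with correlation 0.81,

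overall alpha = 1 − P(|Z1| < 2.807, |Z2| < 2.005) = 0.0460.

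Simulation agrees: 0.0462 for normal statistics (4,000,000 runs) and 0.0461 for t-tests at 50 and then 76 subjects (400,000 runs). The final look thus spends 0.0460 − 0.005 = 0.0410, not 0.045.

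**Step 4. Final level that uses the full 0.05.** Solving 1 − P(|Z1| < 2.807, |Z2| < c) = 0.05 gives c = 1.968, a nominal two-sided level of 0.0491.

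| Interim fraction | Overall alpha with 0.005/0.045 | Final nominal level for overall 0.05 |
|---|---|---|
| 0.50 | 0.0470 | 0.0481 |
| 0.658 (50/76) | 0.0460 | 0.0491 |
| 0.70 | 0.0458 | 0.0493 |
| 0.80 | 0.0453 | 0.0497 |

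**Step 5. Effect on power (noncentral t, 38 per group, final test alone).**

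| Reduction | At 0.045 | At 0.0491 | Gain |
|---|---|---|---|
| 40% | 82.8% | 83.8% | 1.0 point |
| 43.8% | 89.0% | 89.7% | 0.7 point |

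Counting rejection at either look (normal approximation) gives 84.0% against 84.8%, and 89.9% against 90.5%: gains of 0.9 and 0.6 points.

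**The case against.** The best defence is that the stated aim is study-wise Type I error control, and the rule achieves it. No figure in the section is miscalculated. Any scheme whose cumulative spending stays within the overall level is valid, and this one spends 0.005 and then about 0.041. Since 0.005 + 0.045 = 0.05, the overall level cannot exceed 0.05 whatever the correlation between looks. That robustness has some value here: the final size is only approximate, and section 8.3.1 allows a change to survival analysis if many subjects withdraw before discharge, after which subject count would no longer measure information. The 0.05 target and the derivation by subtraction are both inferences. The SAP may also name the spending function.

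Most of this stands. It makes the point one of consistency and efficiency, not validity. It does not remove the point, because the protocol itself fixes the final critical value, so detail in the SAP would not cure the mismatch.

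One could also read 0.045 as the alpha to be spent at the final look, which would give an overall 0.05. The text ties 0.045 to the critical value, however, and the stated powers match a nominal 0.045 (82.8% and 89.0%) rather than 0.0491 (83.8% and 89.7%, which would round to 84% and 90%).

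Two stronger readings are tempting and not supported. A reader might infer that the false-positive rate is inflated; it is about 0.046, below 0.05. A reader might infer that the power figures are wrong; they are correct for the level the protocol states.

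**Conclusion.** The point holds as a low-severity mismatch between the named method and the fixed boundary. The 0.005/0.045 pair is a valid but conservative Bonferroni-type split. Relative to a 0.05 design it leaves about 0.004 of alpha unused (0.05 − 0.046), and a conclusion would change only for a final p-value between 0.045 and about 0.049.

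This rests on an intended overall two-sided alpha of 0.05 (not stated, but the levels sum to it exactly), information proportional to subject numbers with the interim at 50 of 76, and a single primary comparison of pooled active against placebo at two looks. A futility rule, if added, would only lower the Type I error further.

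**What to change.** Either of two small text changes in section 8.3.2 would do, made before any unblinded efficacy look.

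1. **Make the boundary follow the method.** State the overall two-sided alpha (0.05 if that is the intention), keep 0.005 at the interim, and set the final critical value from the joint distribution of the two statistics at the actual information fraction. At 50 of 76 this is about 0.049 two-sided (z = 1.968); over fractions 0.5 to 0.8 it runs from 0.048 to 0.050. Restate power at that level: 83.8% for a 40% reduction and 89.7% for 43.8%.
2. **Make the description follow the boundary.** If 0.045 is kept on purpose, call it a Bonferroni split with overall alpha of at most 0.05 and drop the reference to alpha spending. The power figures then stand as they are.

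The first option needs one boundary calculation and no extra subjects. It has a small price: the final level then depends on the information fraction, which must be recomputed if the survival analysis in section 8.3.1 replaces the ANCOVA, and the split's protection at any correlation is given up. The second option costs only wording, and forgoes the 0.7 to 1 point of power.

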## **9 SPONSOR'S AND INVESTIGATOR'S RESPONSIBILITIES**

This study will be conducted in accordance with current applicable regulations, ICH and local ethical and legal requirements.

## **9.1 Sponsor's Responsibilities**

### **9.1.1 GCP Compliance**

GlycoMimetics, and any third party to whom aspects of the study management or monitoring have been delegated, will undertake their roles for this study in compliance with all applicable regulations and ICH GCP Guideline E6.

Visits to investigator sites will be conducted by representatives of GlycoMimetics or an appropriate designee to inspect study data, subjects' medical records, and CRFs in accordance with current GCP and the respective local and national government regulations and guidelines. Records and data may additionally be reviewed by auditors, interested commercial parties, or by regulatory authorities.

### **9.1.2 Regulatory Approval**

GlycoMimetics will ensure that local regulatory authority requirements are met before the start of the study. GlycoMimetics or an appropriate designee will be responsible for the preparation, submission, and confirmation of receipt of any regulatory authority approvals required prior to release of investigational product for shipment to the study site.

### **9.1.3 Protocol Management**

All protocols and amendments will be prepared by GlycoMimetics. If it becomes necessary to issue a protocol amendment during the course of the study GlycoMimetics or an appropriate designee will notify the investigators and collect documented Investigator Agreements to the amendment.

Any change to this protocol significantly affecting the safety of subjects, the scope of the investigation, or the scientific quality of the study, requires a written protocol amendment that must be approved by the Sponsor, the investigator, and the IRB/IEC before implementation.

Examples of amendments requiring such approval are:

- An increase in drug dosage or duration of exposure of subjects
- A significant change in the study design (eg, addition or deletion of a group or period)
- An increase in the number of invasive procedures to which subjects are exposed
- Addition or deletion of a test procedure for safety monitoring

These requirements for approval should in no way prevent any immediate action from being taken by the investigator or Sponsor in the interest of preserving the safety of all subjects included in the study. If an immediate change to the protocol is felt to be necessary by the investigator and is implemented by him/her for safety

reasons, the Sponsor should be notified within 2 working days and the IRB/IEC should be informed within a reasonable timeframe.

Changes to the protocol affecting only administrative aspects of the study do not require formal protocol amendments or IRB/IEC approval; however, the IRB/IEC must be kept informed of such administrative changes. Examples of administrative changes not requiring formal protocol amendments and IRB/IEC approval include:

- Minor changes in wording (ie, typographical errors, deletion of double-entry words or sentences, adding words for clarification)
- Clarification/modification of procedure instructions
- Change/correction of addresses or phone numbers
- Addition of new clinical sites

#### **9.1.4 Additional Study Sites**

The study may be expanded to additional clinical sites, at the discretion of the Sponsor.

### **9.2 Investigator's Responsibilities**

#### **9.2.1 GCP Compliance**

The investigator must undertake to perform the study in accordance with ICH GCP Guideline E6 and the applicable regulatory requirements.

It is the investigator's responsibility to ensure that adequate time and appropriate resources are available at the study site prior to commitment to participate in this study.

The investigator will maintain a list of appropriately qualified persons to whom the investigator has delegated significant trial-related tasks. An up-to-date copy of the *curriculum vitae* for the investigator and sub-investigator(s) will be provided to GlycoMimetics or an appropriate designee before starting the study.

If the subject has a primary physician the investigator should, with the subject's consent, inform them of the subject's participation in the trial.

#### **9.2.2 Protocol Adherence**

The investigator must adhere to the protocol as detailed in this document. The investigator will be responsible for enrolling only those subjects who have met protocol eligibility criteria.

It is the investigator's responsibility to communicate with his/her local IRB/IEC to ensure accurate and timely information is provided at all phases during the study. In particular the appropriate approvals must be in place prior to recruitment, notification of any SAEs during the study must take place and the IRB/IEC must be informed of study completion.

### **9.3 Documentation and Retention of Records**

#### **9.3.1 Case Report Forms**

CRFs will be supplied by GlycoMimetics or an appropriate designee and should be handled in accordance with instructions from GlycoMimetics/designee.

The investigator is responsible for maintaining adequate and accurate medical records from which accurate information will be transcribed onto CRFs. CRFs should be filled out completely by the investigator or designee as stated in the site delegation list. All CRFs should be completed in a neat legible manner to ensure accurate interpretation of the data; a black ball-point pen is preferred to ensure the clarity of reproduced copies of all CRFs.

All requested information must be entered on CRFs. If an item is not available or is not applicable, this fact should be indicated without leaving a blank space. Incorrect entries should be crossed out with a single line.

The CRFs must be reviewed, signed, and dated by the investigator.

Once the study monitor has verified the contents of the completed CRF pages against the source data, the duplicate pages will be collected and forwarded to GlycoMimetics or an appropriate designee for data entry. Queries may be raised if the data are unclear or contradictory. The investigator or designee must address all queries.

#### **9.3.2 Recording, Access and Retention of Source Data**

Source data to be reviewed during this study will include, but is not limited to: subject's medical file, subject pain cards, original laboratory reports, histology, and pathology reports.

All key data must be recorded in the subject's medical records.

The investigator must permit authorized representatives of GlycoMimetics, the respective national, local or foreign regulatory authorities, the IRB/IEC, auditors, and interested commercial parties to inspect facilities and original records relevant to this study, regardless of media.

The monitor (auditors, IRB/IEC, or regulatory inspectors) may check the CRF entries against the original source documents (regardless of media). The consent form and documents in compliance with applicable privacy regulations (eg, Health Insurance Portability and Accountability Act authorization [HIPAA] and Personal Information Protection and Electronic Documents Act [PIPEDA]) will include a statement by which the subjects allow the monitor/auditor/inspector from GlycoMimetics or an appropriate designee, national or local regulatory authorities, or the IRB/IEC access to source data (eg, subject's medical file, appointment books, original laboratory reports, X-rays, etc.) which substantiate information

recorded in the CRFs. The informed consent form (and assent, where applicable) and applicable authorizations to disclose private information should be worded to ensure the above listed entities access to the essential documents for the entire retention period described below.

As described in the ICH GCP Guidelines, 'essential documents', including CRFs, source documents, consent forms, laboratory test results, and investigational product inventory records, should be retained by the investigator until at least 2 years after the last approval of a marketing application in an ICH region and until there are no pending or contemplated marketing applications in an ICH region or at least 2 years have elapsed since the formal discontinuation of clinical development of the investigational product. These documents should be retained for a longer period however if required by the applicable regulatory requirements or by an agreement with GlycoMimetics.

These records must be made available at reasonable times for inspection and duplication, if required, by a properly authorized representative of the US FDA in accordance with the US Code of Federal Regulations (CFR) 21 CFR 312.68, or by Health Canada or other national or foreign regulatory authorities.

### **9.3.3 Investigational Product Accountability**

All investigational product required for completion of this study will be provided by GlycoMimetics. The recipient will acknowledge receipt of the investigational product indicating shipment content and condition. Damaged supplies will be replaced. Accurate records of all investigational product dispensed, used, and returned, and if applicable, destroyed, will be maintained.

### **9.3.4 Audit/Inspection**

To ensure compliance with relevant regulations, data generated by this study must be available for inspection upon request by representatives of national and foreign regulatory authorities, GlycoMimetics or an appropriate designee, interested commercial parties and the IRB/IEC for each study site.

## **9.4 Ethical Considerations**

This study will be conducted in accordance with the US CFR 21, local, state, and national regulations and ICH guidelines.

### **9.4.1 Informed Consent**

It is the responsibility of the investigator to obtain written informed consent (and assent, where applicable) from subjects. All consent and assent documentation must be in accordance with applicable regulations and ICH E6. Each subject or the subject's legally authorized representative is requested to sign the subject informed consent form (as a certified translation, if applicable) after the subject has received and read the written subject information and received an explanation

of what the study involves, including but not limited to: the objectives, potential benefits and risk, inconveniences and the subject's rights and responsibilities.

A copy of the informed consent documentation (consent form and assent, where applicable) must be given to the subject or the subject's legally authorized representative. If applicable, it will be provided in a certified translation of the local language. Signed consent forms must remain in each subject's study file and must be available for verification by the study monitors at any time.

The investigator will provide the sponsor with a copy of the IRB/IEC approved consent (and assent where applicable) forms, and a copy of the IRB/IEC's written approval, prior to the start of the study.

The sponsor reserves the right to delay initiation of the study at a site where the informed consent (and assent, where applicable) forms do not meet the standards of applicable regulations and ICH E6.

#### **9.4.2 IRB/IEC Approval**

It is the responsibility of the investigator to submit this protocol, the informed consent document, relevant supporting information, and all types of subject recruitment information to the IRB/IEC for review, and all must be approved prior to study initiation at that site. Prior to implementing changes in the study, GlycoMimetics and the IRB/IEC must also approve any revised informed consent documents and amendments to the protocol.

Investigational product supplies will not be released and the subject recruitment may not begin until written approval from the IRB/IEC to proceed with the study has been received by GlycoMimetics or an appropriate designee.

The investigator is responsible for keeping the IRB/IEC aware of the progress of the study and of any changes made to the protocol, but in any case at least once a year. The investigator must also keep the local IRB/IEC informed of any serious and significant adverse events.

